3.1. Study Rationale

This study is being conducted based on the need to identify new and effective antibiotic treatment options for gonorrhea as antimicrobial resistance continues to rise worldwide (see Section 3.2) and based on the results of an open-label, dose-ranging Phase II study of gepotidacin for the treatment of adults with uncomplicated urogenital gonorrhea caused by NG.

Study BTZ116576 was a Phase II, randomized, multicenter, open-label, dose-ranging study evaluating the efficacy, safety, and tolerability of gepotidacin therapy in adult participants with uncomplicated urogenital gonorrhea caused by NG. Participants were administered single oral doses (1500 or 3000 mg) of gepotidacin on Day 1 with a Test-of-Cure (TOC) (Day 4 to 8) Visit. A total of 69 participants (1500 mg: 30 participants; 3000 mg: 39 participants) were included in the Microbiologically Evaluable Population. The primary aim of the study was to provide evidence for 95% bacterial eradication of urogenital NG in the Microbiologically Evaluable Population at the TOC Visit (cure rate) and to exclude the null hypothesis that the cure rate was 80% or less. Microbiological success was achieved by 97% and 95% of participants (lower 1-sided exact 95% confidence interval [CI] bound, 85.1% and 84.7%, respectively) in the 1500- and 3000-mg treatment groups, respectively. Microbiological success (bacterial eradication) was also evaluated for pharyngeal and rectal NG, with 1 of the 2 participants with pharyngeal NG and all 3 participants with rectal NG achieving microbiological success. In Study BTZ116576, gepotidacin was active in vitro

against the 69 baseline urogenital NG isolates recovered, with a gepotidacin minimum inhibitory concentration (MIC) range of ≤ 0.06 to $1 \mu\text{g/mL}$ and 50th and 90th percentile minimum inhibitory concentration (MIC_{50} and MIC_{90}) values of 0.12 and $0.5 \mu\text{g/mL}$, respectively. Additional study results demonstrated that some baseline urogenital NG isolates were resistant to ciprofloxacin, penicillin, and/or tetracycline.

This Phase III study (BTZ116577) aims to evaluate oral gepotidacin compared to intramuscular (IM) ceftriaxone plus oral azithromycin, a currently recommended treatment regimen, for the treatment of uncomplicated urogenital infection caused by NG in adolescent and adult participants.

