5.2. Number of Participants

Approximately 620 participants will be screened and randomized to achieve approximately 400 participants with culture-confirmed urogenital gonorrhea in the Microbiological Intent-to-Treat (micro-ITT) Population, for an estimated total of 200 participants per treatment group in the micro-ITT Population. Enrollment will continue until the target number of participants in the micro-ITT Population has been reached.

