6.1. Inclusion Criteria

Participants are eligible to be included in the study only if all of the following criteria apply:

Age and Weight

1. The participant is ≥ 12 years at the time of signing the informed consent/assent and has a body weight >45 kg.

Note: Although participants as young as 12 years may enroll in the study, study sites must follow their institutional ethics committee and local country/national regulatory guidelines and enrollment will be contingent upon such approvals regarding the allowed lower age limit for clinical study participants.

Type of Participant and Disease Characteristics

2. The participant has clinical suspicion of a urogenital gonococcal infection (which can include sexual contact within the past 14 days with a partner who has a confirmed gonococcal infection) with or without pharyngeal and/or rectal gonococcal infection and has 1 of the following:

- male participants with purulent yellow, green, or white urethral discharge or female participants with abnormal cervical or vaginal mucopurulent discharge upon physical examination

OR

- a prior positive culture for NG from up to 5 days before Screening (as long as the participant has not received any treatment for this infection), or
- a Gram or equivalent stain (urogenital specimens only) positive or presumptive for intracellular diplococci from up to 5 days before Screening (as long as the participant has not received any treatment for this infection), or
- a prior positive NAAT assay for NG from up to 7 days before Screening (as long as the participant has not received any treatment for this infection).

Note: A urogenital specimen will be taken from **all** participants (males and females) for NG culture at the Baseline Visit; however, these results will not be used to determine participant eligibility for enrollment in the study. The culture results will be used to identify the primary analysis population.

3. The participant must be willing to abstain from anal, oral, and vaginal sexual intercourse or use condoms for all forms of intercourse from the Baseline Visit through the TOC Visit.

Sex

4. Male or female and must have his or her original urogenital anatomy at birth

- a. **Male participants:**

- A male participant must agree to use contraception as detailed in Appendix 6 of this protocol from the Baseline Visit through completion of the TOC Visit.

- b. **Female participants:**

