9.1.2. NAAT Assay

Refer to the laboratory manual for local versus central laboratory details and the number and type of specimens to collect for NAAT assay. See Table 2 for collection of NAAT assay samples.

Pretreatment urogenital specimens will be obtained from all participants for NAAT assay to detect the presence of NG, Mgen, and CT nucleic acids at the Baseline Visit. Urogenital specimens will also be obtained from all participants for NAAT assay to detect the presence of NG and CT nucleic acids at the TOC Visit. At the Follow-up Visit, a urogenital specimen for NAAT assay will be collected for detection of Mgen only from participants who had a positive NAAT assay for Mgen at Baseline.

In addition, pretreatment baseline pharyngeal and rectal specimens for NAAT assay for detection of NG and CT will be obtained from participants who are willing to provide such specimens, regardless of known exposure. Specimens will also be collected for NAAT assay for detection of NG and CT at the TOC Visit from all body sites collected at the Baseline Visit. At the Follow-up Visit, a pharyngeal specimen for NAAT assay will be collected for detection of NG and CT from participants whose NAAT assay had the presence of nucleic acid for NG at **both** Baseline and TOC.

The NAAT assay will be performed at a designated laboratory(ies). Participants testing positive for CT or Mgen nucleic acid by NAAT assay at the Baseline Visit should be treated per local standard of care at or after the TOC Visit or at the Follow-up Visit (if treatment has not already been initiated), as required, after all study procedures for the visit have been completed.

Only those participants who have NG or Mgen nucleic acid detected from their baseline NAAT specimen will be evaluated for NAAT outcome and response. The NAAT outcome and response to study treatment will be determined by an algorithm at GSK before breaking of the study blind (**Note:** Sponsor is blinded to participant treatment assignment; see Section 7.4).

For the exploratory objectives, the NAAT outcome is determined by comparing the baseline NAAT result with the respective NAAT result at each subsequent visit. The corresponding NAAT response (success or failure) “by participant” will then be assigned, as shown in Table 6 and Table 7.

Table 6 Determining NAAT Outcome and Response at the Test-of-Cure Visit (NG Only)

Defining Criteria	NAAT Outcome	NAAT Response

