10.2. Sample Size Determination

10.2.1. Justification of Sample Size

Approximately 400 participants will be needed for the primary analysis population (i.e., the micro-ITT Population, as defined in Section 10.3) to demonstrate efficacy of gepotidacin in this study.

A conservative estimate of a 90% microbiological success rate has been assumed for ceftriaxone 500 mg IM plus azithromycin 1 g orally. Participants not returning for TOC will be considered a microbiological failure in this study.

Assuming a 90% microbiological success rate of ceftriaxone plus azithromycin and the same value for the actual success rate of gepotidacin, a sample size of 400 urogenital microbiological evaluable participants (200 participants in each treatment) will provide approximately 91% power to demonstrate noninferiority of gepotidacin and ceftriaxone plus azithromycin in adolescents and adults with uncomplicated gonorrhea caused by NG with a 0.025 one-sided significance level and a -10% noninferiority margin.

Approximately 620 participants will be enrolled and randomized 1:1 to gepotidacin and ceftriaxone plus azithromycin in order to identify approximately 400 participants that meet the definition of the micro-ITT Population.

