Micro-ITT Rectal Population	
 • Participants who meet the definition of the Micro-ITT Population and have confirmed NG isolated that is ceftriaxone susceptible from baseline culture of their rectal specimen. • Participants will be analyzed according to their randomized study treatment. 	
 • Efficacy
Micro-ITT Pharyngeal Population	
 • Participants who meet the definition of the Micro-ITT Population and have confirmed NG isolated that is ceftriaxone susceptible from baseline culture of their pharyngeal specimen. • Participants will be analyzed according to their randomized study treatment. 	
 • Efficacy
Microbiologically Evaluable (ME) Population	
 • Participants who meet the definition of the Micro-ITT Population and follow important components of the study (i.e., (1) receive all planned doses as randomized and actual treatment is the same as randomized, (2) have a urogenital specimen collected at the TOC Visit, with available culture results, (3) have not taken any other systemic antibiotic prior to TOC, unless it was taken for the current infection, and (4) have no major deviation that prevents evaluation of efficacy). • Participants will be analyzed according to their randomized treatment arm. 	
 • Efficacy
Microbiologically Evaluable (ME) Rectal Population	
 • Participants who meet the definition of the Micro-ITT Rectal Population and follow important components of the study (i.e., (1) receive all planned doses as randomized and actual treatment is the same as randomized, (2) have a Rectal specimen collected at the TOC Visit, with available culture results, (3) have not taken any other systemic antibiotic prior to TOC, unless it was taken for the current infection, and (4) have no major deviation that prevents evaluation of efficacy). • Participants will be analyzed according to their randomized treatment arm. 	
 • Efficacy

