ME NAAT TOC Pharyngeal Population	
 Participants who meet the definition of the Micro-ITT Pharyngeal Population and follow important components of the study and were NG NAAT positive for Pharyngeal specimen at baseline (i.e., (1) receive all planned doses as randomized and actual treatment is the same as randomized, (2) have a Pharyngeal NAAT specimen collected at the TOC Visit, with available NAAT results, (3) have not taken any other systemic antibiotic prior to TOC, unless it was taken for the current infection, and (4) have no major deviation that prevents evaluation of efficacy). Participants will be analyzed according to their randomized treatment arm. 	
 Efficacy
ME NAAT FU Mgen Population	
 Participants who meet the definition of the Micro-ITT and follow important components of the study and were Mgen (urogenital) NAAT positive at baseline (i.e., (1) receive all planned doses as randomized and actual treatment is the same as randomized, (2) have Mgen (urogenital) NAAT specimen collected at 	
 Efficacy

Population	Definition / Criteria	Analyses Evaluated
	
the FU Visit, with available NAAT results, (3) have not taken any other systemic antibiotic prior to FU, unless it was taken for the current infection, and (4) have no major deviation that prevents evaluation of efficacy).
 
 Participants will be analyzed according to their randomized treatment arm. 	
ME NAAT FU Pharyngeal Population	
 Participants who meet the definition of the Micro-ITT Pharyngeal Population and follow important components of the study and were NG (pharyngeal) NAAT positive at baseline and TOC (i.e., (1) receive all planned doses as randomized and actual treatment is the same as randomized, (2) have a NG (pharyngeal) NAAT specimen collected at the FU Visit, with available NAAT results, (3) have not taken any other systemic antibiotic prior to FU, unless it was taken for the current infection, and (4) have no major deviation that prevents evaluation of efficacy). Participants will be analyzed according to their randomized treatment arm. 	
 Efficacy

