7.2. Secondary Efficacy Analyses

The secondary clinical questions of interest are: What is the treatment effect on each of the secondary efficacy endpoints after treatment with two doses of gepotidacin 3000 mg, 10-12 hours apart, compared to a single IM 500-mg dose of ceftriaxone plus a single oral 1-g dose of azithromycin in participants with uncomplicated gonorrhea at the body site of interest (rectal/pharyngeal) who have a confirmed NG isolated from baseline culture of their body site (rectal/pharyngeal) specimen. For clarification this population are also required to be ceftriaxone susceptible. Receipt of systemic antimicrobials impacts the endpoint definition. Further details of the estimands for secondary efficacy endpoints are given in Section 2.2. The statistical analyses of all secondary efficacy endpoints will be descriptive in nature, and therefore, will not be subject to multiplicity adjustments.

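### The Mgen clearance analysis is limited to participants with a ceftriaxone-susceptible urogenital NG culture, a condition that the Mgen objective does not contain and the SAP does not justify

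*SAP*

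**What the plan says.** **Objective.** Protocol Section 4 and SAP 2.2 list an exploratory objective on clearance or persistence of Mgen nucleic acid in urogenital specimens, read at Follow-up. The only limit in the endpoint concerns other systemic antimicrobials taken at or after Test-of-Cure (TOC). The estimand tables (Protocol Table 3, SAP Table 1) have no Mgen row.

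**Who is sampled and evaluated.** Protocol 9.1.2 takes a baseline urogenital Mgen NAAT from everyone and a Follow-up specimen from those positive at baseline. Its evaluation rule reads: "Only those participants who have NG or Mgen nucleic acid detected from their baseline NAAT specimen will be evaluated for NAAT outcome and response". SAP 7.3.1.5 likewise says that participants with Mgen detected at baseline are evaluated at Follow-up. Neither text mentions an NG culture.

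**Who is analyzed.** SAP Section 4 admits to Micro-ITT only dosed participants with a confirmed, ceftriaxone-susceptible NG isolate from baseline urogenital culture. It defines the ME NAAT FU Mgen Population as "Participants who meet the definition of the Micro-ITT and follow important components of the study and were Mgen (urogenital) NAAT positive at baseline", with further evaluability conditions. The table of planned analyses in SAP 7.3.1.5 gives these two populations, and no other, for Mgen. Tables 2.338 and 2.339 in SAP Appendix 9 follow it.

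**The concern.** Growth of NG in urogenital culture, and the susceptibility of that NG to ceftriaxone, say nothing about whether a participant carries Mgen or clears it. Participants are treated before culture results are known, and Protocol 6.1 allows entry on clinical suspicion with discharge on examination. A participant can therefore be randomized, dosed, Mgen-positive at baseline and sampled for Mgen at Follow-up, yet have no NG isolate. That participant answers the Mgen question as well as any other but enters no Mgen success-rate table.

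At stake is precision in a dataset that is likely to be small, and agreement between the SAP's description of who is evaluated and its list of who is analyzed.

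**Working it through.** **1. The plan's own figures.** Protocol 5.2: "Approximately 620 participants will be screened and randomized to achieve approximately 400 participants with culture-confirmed urogenital gonorrhea". Protocol 10.2.1: "a sample size of 400 urogenital microbiological evaluable participants (200 participants in each treatment) will provide approximately 91% power". With 90% success in both arms, a 10-point margin and one-sided 0.025:

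Φ(0.10 / √(2 × 0.9 × 0.1 / 200) − 1.96) = Φ(0.10 / 0.03 − 1.96) = Φ(1.373) = 91.5%

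This agrees with the stated 91%; exact enumeration of the unstratified Miettinen-Nurminen test gives 90.0%. The 400 is thus sized for the primary urogenital endpoint, and the documents give no sizing for Mgen.

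**2. Share outside Micro-ITT.** (620 − 400) / 620 = 220 / 620 = 35.5% of planned randomized participants.

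**3. Share of Mgen-positives left out.** The documents give no Mgen prevalence, inside or outside Micro-ITT. Let q be positivity among the 220 divided by positivity among the 400 (an assumption, varied below).

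- Share of baseline Mgen-positives omitted: 220q / (400 + 220q)
- Width of the current CI relative to the CI without the restriction: √((400 + 220q) / 400) = √(1 + 0.55q)

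| q | Positives omitted | Current CI wider by |
|---|---|---|
| 0 | 0% | 0% |
| 0.5 | 110/510 = 21.6% | √1.275 − 1 = 13% |
| 1 | 220/620 = 35.5% | √1.55 − 1 = 24% |
| 1.5 | 330/730 = 45.2% | √1.825 − 1 = 35% |

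The CI column assumes that response rates, the balance between arms and the fraction evaluable at Follow-up are the same inside and outside Micro-ITT.

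**4. Illustrative counts at q = 1.** If 5% to 20% were Mgen-positive at baseline (assumed), there would be 31 to 124 positives among 620 and 20 to 80 among 400, both arms together.

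**5. What makes the evaluable numbers smaller.** Protocol Table 7 and SAP Table 4 say that participants given other systemic antimicrobials before Follow-up are not evaluated there. A bullet in SAP 7.3.1.5 instead classes those treated on or after TOC as unable to determine. Under the endpoint definition they do not contribute, so the counts in step 4 are upper limits. The 220 may also include participants who were never dosed, and these would stay out under the fix.

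**The case against.** **The protocol wording is a necessary condition, and exploratory detail is left to the SAP.** This is right: "only those" with Mgen detected does not promise that all of them are analyzed, and Protocol 10.4.2 delegates exploratory analyses. There is no protocol breach. However, SAP 7.3.1.5 says in its own words that Mgen-positive participants are evaluated, and then restricts them in its table without a reason.

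**The data remain visible.** Baseline Mgen results are summarized among the disease characteristics in ITT (Table 1.305), and central NAAT results are listed in ITT (Listing 603). This stands, but the listing of NAAT outcomes and responses (Listing 602) and both outcome tables are tied to Micro-ITT.

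**The trial is about culture-confirmed gonorrhea.** This is a fair reason to keep the Micro-ITT-based result in view. It is no reason to make it the only one, since no estimand ties the Mgen objective to that population.

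**Two stronger readings are tempting and are not supported.**

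- *That the rectal and pharyngeal analyses have the same fault.* A reader might set the Micro-ITT Rectal definition, "Participants who meet the definition of the Micro-ITT Population and have confirmed NG isolated that is ceftriaxone susceptible from baseline culture of their rectal specimen", against the SAP 7.2 question, "in participants with uncomplicated gonorrhea at the body site of interest (rectal/pharyngeal) who have a confirmed NG isolated from baseline culture of their body site", and note that the prior-NAAT entry route ("a prior positive NAAT assay for NG from up to 7 days before Screening") names no body site. But Protocol Table 3 and SAP Table 1 define these populations as urogenital plus rectal, or urogenital plus pharyngeal, gonorrhea. SAP 7.2.3 and Protocol 10.3 and 10.4.2 agree. Every entry route also sits under clinical suspicion of urogenital infection. The restriction is the prespecified estimand. A set of participants positive only outside the urogenital site would be a change of scope, and its size is unknown and could be zero.
- *That samples from about 35% of participants are thrown away.* The 35.5% is a planned share of randomized participants. Rectal and pharyngeal swabs are optional, Follow-up Mgen specimens come only from baseline positives, and the results stay in ITT displays.

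**Conclusion.** The point holds for Mgen only. The SAP applies an NG culture and susceptibility condition to an objective that does not involve NG, against its own statement of who is evaluated, and gives no rationale. The share of baseline Mgen-positives omitted from success-rate comparisons lies between 0 and 45% for relative positivity from 0 to 1.5. It is 35%, with a CI about 24% wider, only if positivity is equal inside and outside Micro-ITT, which the documents neither state nor contradict.

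The consequence is modest. The analysis is exploratory and descriptive, without formal testing (SAP 7.3), so the primary analysis, its power and type I error are untouched. It is worth correcting because the added precision comes from specimens that the protocol already collects.

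**What to change.** - In SAP Section 4, define the ME NAAT FU Mgen Population from all treated participants with a positive baseline urogenital Mgen NAAT, analyzed as randomized, keeping its other evaluability conditions.
- In the SAP 7.3.1.5 table, and for the Mgen rows only of Tables 2.338 and 2.339, use that base and show the Micro-ITT-based result beside it. Leave the pharyngeal NG rows unchanged.
- If the sponsor prefers to keep the restriction, state the reason in SAP 7.3.1.5 and align the sentence on who is evaluated.

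SAP Section 4 settles population inclusion before unblinding, so the amendment belongs before that point. If unblinding has already taken place, label the wider summary post hoc.

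The cost is one population definition and a rerun of existing shells, with no new visits or specimens. The downside is one more descriptive summary, which includes participants without culture-confirmed gonorrhea; showing both results makes that plain.

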4.1. Protocol Deviations

Important protocol deviations (including deviations related to study inclusion/exclusion criteria, conduct of the trial, participant management or participant assessment) will be summarized and listed. In addition, important deviations which result in exclusion from analysis populations will be listed.

Protocol deviations will be tracked by the study team throughout the conduct of the study in accordance with the Protocol Deviation Management Plan, entitled Study Deviation Rules Document.

- Data will be reviewed prior to unblinding and locking the database to define all analysis populations, and thus ensure all important deviations and deviations which may lead to exclusion from the analysis are captured and categorized in the protocol deviations dataset.
- This dataset will be the basis for the summaries and listings of important protocol deviations.

A separate listing of all inclusion/exclusion criteria deviations will also be provided. This listing will be based on data as recorded on the inclusion/exclusion page of the electronic case report form (eCRF).

5. CONSIDERATIONS FOR DATA ANALYSIS AND DATA HANDLING CONVENTIONS

5.1. Study Treatment & Sub-group Display Descriptors

Treatment Group Descriptions	
Data Displays for Reporting	
Description	Order in TFL
Gepotidacin 2x 3000 mg	1
Ceftriaxone 500 mg plus azithromycin 1 g	2

Note: Total across treatment groups will be presented for study population, safety, and selected microbiology displays.

Whilst the scientific formatting requirements for bacterial nomenclature is for genus and species names to be italicized, with first letter of genus upper case, and rest of the genus and species name in lower case, system limitations have resulted in the lack of italicization in TFL outputs.

